## **3.2    DISCUSSION OF TRIAL DESIGN, INCLUDING THE CHOICE OF CONTROL GROUP**

The primary objective of this trial is to determine the MTD. The most important secondary objective is to assess the safety of BI 836826. This can be achieved by an open-label, single arm trial design without a control group.

The investigational drug BI 836826 will be administered as monotherapy. At the lowest dose cohorts, single patients are to be enrolled to limit the number of patients who are receiving doses of the drug which may not exert a relevant pharmacodynamic effect in humans. Stipulated by drug related adverse events CTCAE grade 2 or higher, cohorts of single patients will be expanded to cohorts of at least 3 patients as described in section [3.1](#), and the trial design will follow a standard 3+3 design with dose-escalation and de-escalation. According to the interim safety analysis of the trial results, the MTD was defined for Caucasian patients to be 100 mg. Once the MTD has been defined for Asian patients the enrollment will be stopped. Given the recent safety signals at 100 mg, the current expansion cohort at MTD of 100 mg will be closed for enrollment after having enrolled 4 patients from S Korea, and a new, small cohort will be open to test the 50 mg and 75 mg dose in Korean patients.

At screening, blood samples are drawn, a physical examination and a routine CT scan are performed, and the patient is evaluated for eligibility in the trial. Bone marrow aspirate/biopsy may be performed at the discretion of the investigator. In case a bone marrow aspirate/biopsy has been performed after the latest therapy before this trial, it should be recorded.

**Proprietary confidential information.**

**© 2016 Boehringer Ingelheim International GmbH or one or more of its affiliated companies. All rights reserved.**

This document may not - in full or in part - be passed on, reproduced, published or otherwise used without prior written permission.

Clinical disease status will be assessed at screening, at the administration of the first and the last of the 4 infusions and 3 weeks after the last infusion of a respective course with physical examination, clinical assessment of the B-NHL, and blood samples. CT scans in this trial will be performed in accordance with published guidelines for response evaluation in lymphoma ([R04-1585](#)) and correspond to the use in clinical practice ([section 5.1.2.2](#)). A CT scan will be done prior to treatment (may be performed up to 8 weeks (preferably 4 weeks) prior to first infusion), after 2 courses of treatment, (*i.e.* at week 13 +/- window), and just before the end of treatment (EOT) visit (*i.e.* week 25 +/- window). If the CT scans are not possible or available, magnetic resonance imaging can be used instead. However the same imaging methods should be used consistently throughout the trial. Bone marrow examination, PET scan and additional CT scans will be performed at the discretion of the investigator. Results of CT scan, optional PET scan or bone marrow examination performed during the conduct of the trial should be reported in the eCRF. After the EOT visit which may occur at the latest at week 26, the patient will enter the follow-up phase. During the follow-up phase, disease status evaluations (physical examination, clinical assessment of lymphoma, and blood samples) should be performed at least every 6 weeks until 6 months after the EOT visit, administration of new anti-lymphoma therapy or death, whatever occurs first. More frequent visits may be indicated, *e.g.* for follow-up of laboratory parameters or adverse events which have not been resolved at the EOT visit.

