- 3 After informed consent, and review of in- and exclusion criteria, and before the first administration of the trial drug
- 4 For details refer to [section 5.2.3.1](#)
- 5 Screening for tumour lysis syndrome in between safety laboratory assessments ([section 5.2.3.2](#))
- 6 Disease / response assessment will be based on clinical judgement when recent CT is not available
- 7 For women of childbearing potential only (please refer to sections [3.3.3](#) (exclusion criterion 20) and [5.2.3.1](#))
- 8 Quantitative CMV DNA PCR ([section 5.2.3.3.2](#))
  
- 10 Please refer to [section 5.2.3.3.1](#)
- 11 CT scan may be performed up to 4 weeks prior to first infusion according to the standard of care in this patient population

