### 4.2.2 Restrictions

#### 4.2.2.1 Restrictions regarding concomitant treatment

Prior therapies for lymphoma must have been discontinued at least of two weeks before the first administration of the trial drug (see exclusion criteria [section 3.3.3](#) for details) and the patient must have recovered from all clinically relevant reversible toxicities. A time interval

Proprietary confidential information.

© 2016 Boehringer Ingelheim International GmbH or one or more of its affiliated companies. All rights reserved.

This document may not - in full or in part - be passed on, reproduced, published or otherwise used without prior written permission.

of at least four weeks must have elapsed from the last administration of any other investigational treatment for NHL to the first administration of BI 836826.

No anti-neoplastic therapy concomitantly is allowed.

No other investigational therapy concomitantly is allowed.

Additional glucocorticoid medications may be used as clinically indicated to treat infusion-related reactions at any dose. Short term systemic glucocorticoid for lung disease (asthma or COPD) may be used. Daily oral steroid treatment may be administered at doses equivalent to prednisolone 10 mg per day. All other indications for steroids have to be discussed and agreed upon between investigator and sponsor.

Immunoglobulins may not be used within four weeks prior to the first trial infusion and two weeks after the last infusion of BI 836826.

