#### 6.2.1 Screening and run-in period(s)

The screening period, *i.e.* the phase after informed consent and before the first administration of the trial drug, may be as long as 14 days. However, a pre trial CT scan, performed as part of routine clinical practice, can be used as the baseline CT scan given that the CT scan is

Proprietary confidential information.

© 2016 Boehringer Ingelheim International GmbH or one or more of its affiliated companies. All rights reserved.

This document may not - in full or in part - be passed on, reproduced, published or otherwise used without prior written permission.

valid and encompass neck, thorax, abdomen and pelvis, and it should be performed preferably within 4 weeks before visit 1. If the patient has not received any anti lymphoma treatments and regarded as clinical stable by the investigator, the pre trial CT scan within 8 weeks before visit 1 can be employed. Parameters and investigations according to flowchart for course 1 have to be obtained and / or performed, please refer to [flowchart](#) for Course 1.

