6.7 BASELINE, TIME WINDOWS AND CALCULATED VISITS

Study days and visits will be labelled according to the flow chart of the CTP.

Unless otherwise specified, baseline is defined as the time-point closest to but prior to first administration of trial medication in the first treatment phase, where the first administration

of trial medication is defined in [Section 6.3](#) above. If this criterion is not fulfilled, then no baseline will be derived.

For laboratories where not only the examination date but also time is recorded, examination time has to be taken into account when defining baseline. That is, a laboratory value on the same date as the first study drug administration is considered as baseline value if and only if the time of laboratory value is before or the same as the date and time of the start of first study drug administration.

If any of these times are missing (either no time of start of first study drug administration or no lab sample stating that it was taken prior to start of first study drug administration) and so it cannot be concluded whether the blood sampling was done before or at the same time of the start of first study drug administration, the last available laboratory assessment before first study drug administration will be taken (Screening laboratory) .

For graphical presentations of laboratory data, baseline will be coded as Day = 1.

The definition of relative baseline for the investigation of laboratory signs of cell destruction is given in [Section 5.4.5.2](#).

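### The baseline CT window is stated three different ways, and the SAP does not check how old the baseline scan is

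*Protocol*

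**What the plan says.** The protocol gives the age limit for the baseline CT in four places, with three different contents.

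- **Course 1 flowchart, footnote 11, and the split-dose flowchart (10.7.1), footnote 11:** "CT scan may be performed up to 4 weeks prior to first infusion according to the standard of care in this patient population". There is no 8-week option.
- **Section 3.2:** "A CT scan will be done prior to treatment (may be performed up to 8 weeks (preferably 4 weeks) prior to first infusion", with no condition on treatment or disease course.
- **Section 6.2.1:** a routine pre-trial scan can serve as baseline, but "it should be performed preferably within 4 weeks before visit 1". The limit extends to 8 weeks under a condition: "If the patient has not received any anti lymphoma treatments and regarded as clinical stable by the investigator".

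On prior treatment, exclusion criteria 3 and 4 require a gap of 4 weeks before visit 1 for chemotherapy and for non-radiolabelled anti-CD20 therapy. Section 4.2.2.1 sets the general minimum: "Prior therapies for lymphoma must have been discontinued at least of two weeks before the first administration of the trial drug".

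On analysis, SAP section 6.7 says that, unless otherwise specified, "baseline is defined as the time-point closest to but prior to first administration of trial medication in the first treatment phase". SAP sections 5.2.2 and 7.5.2 use baseline imaging for best percentage change in SPD and for the waterfall plot. They also plan a best-response analysis restricted to assessments with imaging data, and a remission rate.

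**The concern.** The baseline scan is the reference for every SPD change and for the 50% fall that defines partial remission (5.1.2.2.3). If it is old, part of the measured change happened before the first infusion. Shrinkage from earlier therapy would be credited to BI 836826. Growth before the first infusion would hide a real fall. The trial has a single arm, so no control group shows or cancels the error.

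With three texts in force, a site cannot tell whether a 7-week-old scan is acceptable, and the SAP would take it without comment if it is the latest one before dosing.

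**Working it through.** **1. The plan's own figures.** The plan computes nothing on this point; its figures are the windows and the treatment gaps above. The sample size counts reproduce (3×1 + 3×3 + 3×6 = 30; 41 + 12 = 53) but play no part here.

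**2. The texts side by side.**

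| Place | Oldest scan allowed | Condition |
|---|---|---|
| Both course 1 flowcharts, footnote 11 | 4 weeks | none |
| Section 3.2 | 8 weeks (4 preferred) | none |
| Section 6.2.1 | 8 weeks (4 preferred) | no anti-lymphoma treatment, clinically stable |

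Take a scan 7 weeks old in a patient whose chemotherapy ended 5 weeks before visit 1. Exclusion criterion 3 is satisfied (5 is not below 4). The scan breaks the flowchart limit and is allowed by 3.2. Under 6.2.1 the answer depends on a period that is not given. The scan precedes the end of chemotherapy by 7 - 5 = 2 weeks.

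**3. Longest time by which the scan can precede the end of prior therapy** = window minus minimum gap.

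| Window | Chemotherapy, anti-CD20 (gap 4 weeks) | General minimum only (gap 2 weeks) |
|---|---|---|
| 8 weeks (3.2 as written) | 8 - 4 = 4 weeks | 8 - 2 = 6 weeks |
| 4 weeks (flowcharts) | 4 - 4 = 0 weeks | 4 - 2 = 2 weeks |

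External radiotherapy is an example of the last column: no exclusion criterion sets an interval for it.

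**4. The condition in 6.2.1.** Taken literally, no eligible patient can meet it, because inclusion criterion 2 requires prior therapy. A meaning such as since the scan has to be supplied. Clinical stability also sits uneasily with inclusion criterion 4, which requires relapse or progression with an indication for therapy.

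**5. Effect on the reading.** The documents give no rate of growth or shrinkage, so the rates here are assumed.

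*Growth before the first infusion.* With scan age a and SPD doubling time d (weeks), a true 50% fall reads as 0.5 × 2^(a/d) - 1.
- a = 8, d = 8: 0.5 × 2.00 = 1.00, reads as 0%.
- a = 8, d = 26: 0.5 × 1.24 = 0.62, reads as -38%.
- a = 4, d = 8: 0.5 × 1.41 = 0.71, reads as -29%.
- a = 4, d = 26: 0.5 × 1.11 = 0.56, reads as -44%.

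All four miss the 50% limit. The two 4-week results do not come from the conflict, since every text permits a 4-week-old scan. Moving from 4 to 8 weeks adds about 6 points (slow growth, -44% to -38%) to 29 points (fast growth, -29% to 0%).

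*Shrinkage from earlier therapy.* If SPD fell by a fraction s between scan and first infusion, the true fall on study drug that reads as 50% is 1 - 0.5/(1 - s).

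| s | 10% | 20% | 30% | 40% | 50% |
|---|---|---|---|---|---|
| True fall needed | 44.4% | 37.5% | 28.6% | 16.7% | 0% |

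**The case against.** The strongest defence is that 6.2.1 governs. Section 3.2 is a design discussion, whereas the lead-in to section 6.2 says its subsections give the detail of the flowchart investigations. Amendment 1 added the 8-week wording to 3.2 and 6.2.1 together, to avoid scans not considered indicated. With its condition read as since the scan, a scan between 4 and 8 weeks old cannot precede intervening therapy. This stands as a sensible reading, and it removes most of the carry-over risk. It does not supply the missing period, and it leaves the 4-week footnotes contradicted. Section 6.2.1 itself refers back to the course 1 flowchart.

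A reader might infer more than the documents support:

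- **That the remission rate is inflated by earlier therapy.** A patient whose nodes are still shrinking markedly is hard to call relapsing or progressing under inclusion criterion 4. The larger values of s in the table are therefore unlikely.
- **That fast growth is typical of patients with an 8-week scan.** Doubling in 8 weeks fits poorly with the stability condition of 6.2.1, if that condition applies.
- **That old scans differ by site or histology.** Nothing in the documents shows this, or how many scans are old.
- **That all response results and PFS or FFS are distorted.** One of the two SAP best-response analyses takes investigator responses however they were assessed. SPD progression is judged from nadir, so it depends on the baseline scan only where that scan is itself the nadir.

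It is also fair to say that SAP 6.7, by taking the closest pre-dose value, favours the newest scan available.

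**Conclusion.** The inconsistency is certain. Its effect on results is possible, in either direction, and unquantified. Under section 3.2 as written the baseline can precede the end of prior therapy by up to 4 or 6 weeks; under the natural reading of 6.2.1 most of that goes. The growth illustration (0% to -38% for a true 50% fall against an 8-week-old scan) rests on the assumed doubling times of 8 to 26 weeks.

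Only best percentage SPD change, imaging-based response and the remission rate are exposed. All are secondary and descriptive, and section 7.2 plans no formal tests. MTD, DLT and sample size are unaffected. Severity: minor.

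**What to change.** **Protocol.** Reconcile 3.2, 6.2.1 and both flowchart footnotes into one stated window. State that a scan can serve as baseline only if no lymphoma therapy was given between it and the first infusion. The second rule is needed in its own right, because even a 4-week window leaves up to 2 weeks of overlap for therapy held only to the general minimum.

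**SAP (5.2.2, 6.7, 7.5.2).**
- List the interval from baseline scan to first infusion for every patient.
- Flag baseline scans more than 28 days old.
- Where dates allow, flag scans that precede the end of prior therapy. Section 5.3.2.1 accepts month and year for chemotherapy and immunotherapy dates, so state a convention for partial dates. For radiotherapy that section specifies only dose and fields, so use an end date only where one was recorded.
- Repeat the SPD, imaging-based best response and remission-rate summaries without flagged patients.

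**Cost.** The scan-age listing needs only the scan date and the first-infusion date, which the SAP baseline rule already requires. With 41 patients enrolled and up to 12 to come (7.6), the wording change helps later entrants only, while the listing and flags cover everyone. A few later patients may need the screening CT instead of an older routine scan. Dose levels hold 1 to 6 patients and measurable disease is required only in the expansion cohort, so the sensitivity summary will show little within a cohort and is best read over all patients.

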### 3.3 SELECTION OF TRIAL POPULATION

#### 3.3.1 Main diagnosis for study entry

The eligible patients for the trial are patients with non-Hodgkin lymphoma of B cell origin, who have progression of disease either after having received high-dose therapy with stem cell support or who are not eligible for high-dose therapy. There is no standard of care for these patients and only minorities of the patients obtain durable responses and/or long progression free intervals with the current available therapies.

#### 3.3.2 Inclusion criteria

1. Patients with relapsed or refractory non-Hodgkin lymphoma of B cell origin (mature B cell lymphoma according to WHO) not considered candidates for intensive anti-lymphoma therapy
2. Patients must have either aggressive NHL and received at least one prior anti-CD20 containing immunochemotherapy or indolent NHL and received anti-CD20 therapy and at least two prior therapies (see [appendix 10.2](#))
  - a. Patients with aggressive NHL who have received at least one prior anti-CD20 containing immunochemotherapy and have
    - i. relapse/progression and is not considered a candidate for high-dose immunochemotherapy with autologous stem cell support or allogeneic transplantation
    - ii. relapse/progression after high-dose immunochemotherapy with autologous stem cell support
    - iii. relapse/progression after allogeneic stem cell transplantation if without

Proprietary confidential information.

© 2016 Boehringer Ingelheim International GmbH or one or more of its affiliated companies. All rights reserved.

This document may not - in full or in part - be passed on, reproduced, published or otherwise used without prior written permission.

immunosuppression for at least 8 weeks and no evidence of active GvHD (this criterion applies only for the expansion cohort)

- b. Patients with indolent NHL who have received anti-CD20 therapy and at least two prior therapies and have
  - i. relapse/progression and is not considered a candidate for high-dose immunochemotherapy with autologous stem cell support or allogeneic transplantation
  - ii. relapse/progression after high-dose immunochemotherapy with autologous stem cell support
  - iii. relapse after allogeneic stem cell transplantation if without immunosuppression for at least 8 weeks and no evidence of active GvHD (this criterion applies only for the expansion cohort)
- 3. Measurable disease on CT scan with involvement of at least one clearly demarcated lesion  $\geq 2$  cm or two or more clearly demarcated lesions of  $>1.5$  cm at longest diameter (this criterion applies only for the expansion cohort)
- 4. Relapse or progression of disease with an indication for therapy as per investigator's judgement
- 5. Life expectancy of  $\geq 3$  months as per investigator's judgement
- 6. ECOG Performance Status 0 or 1 (see appendix [10.3](#))
- 7. Age  $\geq 18$  years
- 8. Written informed consent which is consistent with ICH-GCP guidelines and local legislation

### 3.3.3 Exclusion criteria

- 1. Primary central nervous system (CNS) lymphoma or known CNS involvement
- 2. Prior history of malignancy other than a mature B cell neoplasm according to WHO classification ([R10-6296](#)) (except basal cell or squamous cell carcinoma of the skin, or carcinoma *in situ* of the uterine cervix or breast treated with curative therapy) unless the subject has been free of disease and without treatment for at least 5 years
- 3. Last chemotherapy  $< 4$  weeks prior to visit 1
- 4. Last anti-CD20 therapy (non-radiolabelled)  $< 4$  weeks prior to visit 1
- 5. Last corticosteroid  $< 2$  weeks prior to visit 1 unless the dose is  $\leq 10$  mg/day prednisolone or equivalent
- 6. High-dose therapy with stem cell support  $< 6$  months prior to visit 1
- 7. Radio-immunotherapy  $< 3$  months prior to visit 1
- 8. Prior allogeneic stem cell transplant (this criterion applies only for the dose-escalation cohorts)
- 9. AST or ALT  $> 2.5 \times$  upper limit of normal (CTCAE grade 2 or higher)
- 10. Total bilirubin  $> 1.5 \times$  upper limit of normal (CTCAE grade 2 or higher)
- 11. Absolute neutrophil count  $< 1.0 \times 10^9/L$  (without growth factor support)
- 12. Platelets  $< 25 \times 10^9/L$  (without growth factor support or transfusions)
- 13. Calculated GFR  $< 45$  mL/min (see [appendix 10.5](#))
- 14. Proteinuria CTCAE grade 2 or higher

Proprietary confidential information.

© 2016 Boehringer Ingelheim International GmbH or one or more of its affiliated companies. All rights reserved.

This document may not - in full or in part - be passed on, reproduced, published or otherwise used without prior written permission.

15. Significant concurrent medical disease or condition which according to the investigator's judgement would either compromise patient safety or interfere with the evaluation of the safety of the test drug, *e.g.* symptomatic congestive heart failure, unstable angina pectoris, cardiac arrhythmia requiring therapy with the exception of extra systoles or minor conduction abnormalities
16. Chronic or ongoing infection requiring treatment at the time of enrolment or within the previous two weeks
17. Active hepatitis B or hepatitis C, or laboratory evidence for a chronic infection with hepatitis B or C (see [5.2.3.3.1](#))
18. HIV infection
19. CMV viraemia
20. Women of childbearing potential not using a highly effective method of birth control during the trial until one year after the last dose. Highly effective methods of birth control are defined as those which result in a low failure rate (*i.e.* less than 1% per year) when used consistently and correctly used such as implants, injectables, combined oral contraceptives, some intrauterine devices (IUDs), sexual abstinence or vasectomised partner. Barrier methods of contraception are accepted if condom or occlusive cap is used together with spermicides (*e.g.* foam, gel). Female patients will be considered to be of childbearing potential unless surgically sterilised by hysterectomy or bilateral tubal ligation/salpingectomy, or postmenopausal for at least two years
21. Pregnancy or breast feeding
22. Known or suspected active alcohol or drug abuse as per investigator's judgment
23. Treatment with another investigational drug within the past four weeks before start of therapy or concomitantly with this trial
24. Prior treatment with BI 836826
25. Patients unable to comply with the protocol as per investigator's judgement

### **3.3.4 Removal of patients from therapy or assessments**

#### **3.3.4.1 Removal of individual patients**

A patient has to discontinue trial drug administration in case

- A DLT occurs which does not recover to a degree that allows treatment continuation (see [4.1.4.3](#))
- Progressive disease or any other concomitant diagnosis/symptom develops resulting in an indication to start any other therapy for lymphoma, including deterioration of general condition

An individual patient is to be withdrawn from trial in case

- The patient withdraws consent. Patients are free to discontinue their participation in this trial at any time without the need to justify the decision
- The patient needs concomitant drugs that may interfere with the investigational product (please refer to [section 4.2.2](#))

